**Additional Dose Escalation Parameters (Phase I Only):**

In addition to monitoring for dose limiting toxicity, patients enrolled in the Phase I component will be monitored for signs of immune activation using treatment related tachycardia and fever as clinical markers of transient bioactivity. Refer to [Section 7.1.2](#) Monitoring for Signs of Immune Activation (Phase I patients) for the definition of tachycardia and fever thresholds.

If detected in a single patient (fever or tachycardia lasting > 4 hours OR meets criteria for any DLT) subsequent dose levels will increase by 50% instead of the planned doubling (100% increase). For example, if signs of immune activation occurred at Dose Level 4 (50 µg/kg/day), Dose Level 5 would be adjusted to 75 µg/kg/day rather than 100 µg/kg/day and Dose Level 6 would be 115 µg/kg/day ( $75 \times 1.5$  rounded up to the nearest 5) rather than 200 µg/kg/day.

### **7.2.2 Extended Component (Phase II)**

The treatment schedule is identical to the dose finding component. The extended component uses a Simon's MiniMax two-stage design for continued enrollment using the maximum tolerated dose (MTD) established during Phase I with monitoring guidelines to stop the study early for excessive toxicity.

In Stage 1, a total of 13 patients (including all treated at the MTD in part 1) will be enrolled. If 3 or more of these have clinical response the trial will continue to Stage 2. If the phase I component enrolls more than 13 patients at the MTD, the two-stage design will be adjusted with the given number of patients enrolled at the MTD.

In Stage 2, an additional 17 patients will be enrolled for a total of 30 patients treated at the MTD.

### 7.3 Management of Selected GTB-3550 TriKE Toxicities

Throughout the study, the investigator may prescribe any concomitant medications or treatment deemed necessary to provide adequate supportive care. Supportive care may include antibiotics, anti-fungals, analgesics, transfusions, and G-CSF/cytokines.

Note: Any patient experiencing a DLT equivalent toxicity must discontinue treatment per [Section 7.5](#) and is not eligible for retreatment.

Please refer to [Section 9.7](#) for potential toxicities.

#### 7.3.1 Tumor Lysis Syndrome

Tumor lysis syndrome is a possible risk associated with therapy of active leukemia. All patients (except those with known allergy) will begin on prophylactic allopurinol 300 mg po before the 1st dose of GTB-3550 TriKE and continue daily as clinically indicated.

#### 7.3.2 Infusion Related Reaction

Patients will be monitored for the occurrence of hypotension, dyspnea and angioedema during the infusion. The infusion will be stopped and the reaction treated per [Section 7.1](#). A Grade 3 or Grade 4 infusion related reaction will result in permanent discontinuation of the infusion.

#### 7.3.3 Increase in Liver Function Tests

Liver function tests will be monitored three times weekly during each CI block and at Day 22, 29, and 60 visits.

Elevated liver function tests (ALT, AST and/or total bilirubin) guidelines based on CTCAE v 5 grading:

**Grade 1 or 2:** continue therapy per protocol

**Grade 3:** discontinue treatment for the current block after completion of the currently hung infusion bag, if applicable. Missed doses are not made up.

At the time of next scheduled treatment, if LFTs return to Grade 0 in two weeks or less, initiate the next block of treatment; however, reduce the TriKE dosing by 1 dose level.

**Grade 4 or recurrence of a Grade 3:** permanently discontinue therapy

#### **7.3.4 Neurotoxicity**

A neurological assessment including basic motor (gait), coordination (steadiness) and cognitive function (alert and oriented) should be performed daily during each CI block. Any abnormalities should be followed up with a detailed neurologic exam and appropriate clinical care.

#### **7.3.5 Pulmonary Toxicity**

Patients will be monitored for clinical signs and symptoms of pulmonary toxicity through routine daily patient assessments and via the Targeted Toxicities Worksheet ([Appendix VI](#)). O2 saturation levels will be checked per routine in-patient assessments (minimum of once every nursing shift).

Any new hypoxia will be evaluated with a chest x-ray or other imaging as clinically indicated.

Grade 3 hypoxia (decreased oxygen saturation at rest [e.g., pulse oximeter < 88%]) or higher is a dose limiting toxicity. In this situation, discontinue treatment for per [Section 7.5](#) after completion of the currently hung infusion bag, if applicable.

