**Dose Finding Phase I Component:**

Each patient receives GTB-3550 TriKE at the assigned CI dose for 3 sets (infusion block #1, #2, and #3) of 4 consecutive 24 hours infusions separated by a 72 hour rest.

Dose Level	GTB-3550 TriKE Dose daily continuous infusion (CI) dose ( $\mu\text{g/kg/day}$ )
1	5
2	10
3	25
4	50
5	100
6	150
7	200

The phase I component uses a continual reassessment method (CRM). Patients are enrolled in cohorts of 2 beginning at Dose Level 1. A minimum of 1 week must separate each patient. Both patients within each cohort must reach Day 28 (end of the DLT assessment period) prior to enrollment of a subsequent cohort. The study statistician assigns each new cohort of 2 patients to the most appropriate dose level based on updated toxicity probabilities. As enrollment proceeds, each cohort will be assigned to an increased, decreased or equivalent dose level based on prior data in the trial. Enrollment continues until the study sample reaches evaluable 30 patients. At that time the maximum tolerated dose (MTD) for the Phase II component will be identified.

**Dose Limiting Toxicity (DLT)** is defined as any related treatment emergent toxicity within 28 days (as assessed on Day 29) of the first dose of TriKE with the exception of those that are clearly and incontrovertibly due to extraneous causes for the following criteria based on CTCAE v5:

- Any Grade 4 or 5 non-hematologic events
- Grade 3 non-hematologic adverse events lasting more than 72 hours, except the following:
  - Non-sustained (< 7 days) Grade 3 liver function tests (ALT/AST, alkaline phosphatase, total or direct bilirubin) abnormalities in the absence of clinical signs of hepatic dysfunction (lethargy, confusion, anorexia, pruritus or tremors).
  - Non-sustained Grade 3 QTc prolongation (< 72 hours) in the absence of cardiac arrhythmia
  - Grade 3 electrolyte disturbances that resolve, with or without intervention, to < Grade 2 levels within 72 hours
  - Grade 3 fatigue
  - Grade 3 anorexia
  - Grade 3 fever
  - Grade 3 infection

- Hematologic Toxicity - Given that AML and MDS inherently leads to low neutrophils and platelets, standard grading cannot be used as many of these patients technically meet criteria for “grade 4” neutropenia or thrombocytopenia at baseline. Thus, the hematologic DLTs are listed below:
  - AML:
    - Grade 4 neutrophil count (<500/ $\mu$ L) lasting  $\geq$  29 days from start of cycle in absence of evidence of active leukemia

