## 7.2 GTB-3550 TriKE Dose Levels

### 7.2.1 Dose Finding Component (Phase I)

The 1st two patients will be assigned dose level 1. The study statistician (UMN biostatistician [name] or designee) will assign each new cohort of 2 patients to the most appropriate dose level based on updated toxicity probabilities. Both patients within a dose cohort must reach Day 28 (end of the DLT assessment period) prior to enrollment of a subsequent cohort. Enrollment continues until 30 evaluable patients are accrued.

Dose Level	GTB-3550 TriKE Dose daily continuous infusion (CI) dose ( $\mu$ g/kg/day)
1	5
2	10
3	25
4	50
5	100
6	150
7	200

**Dose Limiting Toxicity (DLT)** is defined as any of the following related treatment emergent toxicity with the exception of those that are clearly and incontrovertibly due to extraneous causes within 28 days (**as assessed on Day 29**) of the first dose of TriKE for the following criteria based on CTCAE v5:

- Any Grade 4 or 5 non-hematologic events
- Grade 3 non-hematologic adverse events lasting more than 72 hours, except the following:
  - Non-sustained (< 7 days) Grade 3 liver function tests (ALT/AST, alkaline phosphatase, total or direct bilirubin) abnormalities in the absence of clinical signs of hepatic dysfunction (lethargy, confusion, anorexia, pruritus or tremors).
  - Non-sustained Grade 3 QTc prolongation (< 72 hours) in the absence of cardiac arrhythmia
  - Grade 3 electrolyte disturbances that resolve, with or without intervention, to < Grade 2 levels within 72 hours
  - Grade 3 fatigue
  - Grade 3 anorexia
  - Grade 3 fever
  - Grade 3 infection
- Hematologic Toxicity - Given that AML and MDS inherently leads to low neutrophils and platelets, standard grading cannot be used as many of these patients technically meet criteria for "Grade 4" neutropenia or thrombocytopenia at baseline. Thus, the hematologic DLTs are listed below:
  - AML
    - Grade 4 neutrophil count (< 500/ $\mu$ L) lasting  $\geq$  29 days from start of cycle in absence of evidence of active leukemia
    - Grade 4 platelet count (< 25,000/ $\mu$ L) lasting  $\geq$  29 days from start of cycle in absence of evidence of active leukemia
- Any clinically significant bleeding that is not controllable with transfusion support
  - MDS/mast cell diseases:
    - Grade 4 neutrophil count (<500/ $\mu$ L) lasting  $\geq$  29 days from start of cycle in absence of evidence of active MDS/mast cell disease

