    - Grade 4 platelet count (<25,000/ $\mu$ L) lasting  $\geq$  29 days from start of cycle in the absence of active MDS/Mast cell disease
    - Any clinically significant bleeding that is not controllable with transfusion support
    - Grade 4 anemia, unexplained by the underlying disease

- Grade 3 infusion related, treatment related reaction including cytokine release syndrome which does not resolve within 72 hours despite best medical management (refer to [Section 10](#) for modified CRS grading)
- Grade 3 or 4 Tumor Lysis Syndrome that does not resolve within 7 days with or without intervention
- Inability to complete at least one block of three 24 hour infusions due to any treatment emergent, treatment related toxicity.

**Maximum Tolerated Dose (MTD)** is defined as the dose level that most closely corresponds to the target DLT rate of 20%.

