### **10.3 Dose Limiting Toxicity Documentation and Reporting (Phase I Dose Finding)**

The following events count toward dose limiting toxicity (DLT) during the Phase I dose finding component and must be reported the UMN Multisite Program Manager per [Section 10.6](#).

Note: DLT events are only reported for patients enrolled in the Phase I portion of the trial; however, any patient experiencing a DLT is not eligible to continue treatment per [Section 7.5](#).

A DLT is defined as a related treatment emergent toxicity that occurs within 28 days after the 1st TriKE dose with the exception of those that are clearly and incontrovertibly due to extraneous causes:

- Any Grade 4 or 5 non-hematologic events
- Grade 3 non-hematologic adverse events lasting more than 72 hours, **except** the following:
  - Non-sustained (< 7 days) Grade 3 liver function tests (ALT/AST, alkaline phosphatase, total or direct bilirubin) abnormalities in the absence of clinical signs of hepatic dysfunction (lethargy, confusion, anorexia, pruritus or tremors).
  - Non-sustained Grade 3 QTc prolongation (< 72 hours) in the absence of cardiac arrhythmia
  - Grade 3 electrolyte disturbances that resolve, with or without intervention, to < Grade 2 levels within 72 hours
  - Grade 3 fatigue
  - Grade 3 anorexia
  - Grade 3 fever
  - Grade 3 infection
- Hematologic Toxicity - Given that AML and MDS inherently leads to low neutrophils and platelets, standard grading cannot be used as many of these patients technically meet criteria for “grade 4” neutropenia or thrombocytopenia at baseline. Thus, the hematologic DLTs are listed below:
  - AML
    - Grade 4 neutrophil count (< 500/ $\mu$ L) lasting  $\geq$  29 days from start of cycle in absence of evidence of active leukemia

- Grade 4 platelet count (< 25,000/ $\mu$ L) lasting  $\geq$  29 days from start of cycle in absence of evidence of active leukemia
- Any clinically significant bleeding that is not controllable with transfusion support
- MDS/mast cell diseases:
  - Grade 4 neutrophil count (<500/ $\mu$ L) lasting  $\geq$  29 days from start of cycle in absence of evidence of active MDS/mast cell disease
  - Grade 4 platelet count (<25,000/ $\mu$ L) lasting  $\geq$  29 days from start of cycle in the absence of active MDS/Mast cell disease
  - Any clinically significant bleeding that is not controllable with transfusion support
  - Grade 4 anemia, unexplained by the underlying disease

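### Short Grade 3 hypoxia, a stop after three Block 1 infusions, and the trigger for the 50% dose step are each defined differently in different places

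*Combined protocol and SAP*

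**What the plan says.** **Hypoxia.** Section 7.3.5 states that Grade 3 hypoxia "or higher is a dose limiting toxicity" and orders discontinuation under Section 7.5 "after completion of the currently hung infusion bag, if applicable". It sets no duration and does not mention relatedness.

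**DLT definition.** Section 7.2.1 covers "any of the following related treatment emergent toxicity" within 28 days of the first dose. One criterion, worded alike in the Study Schema, 7.2.1 and 10.3, is "Grade 3 non-hematologic adverse events lasting more than 72 hours, except the following". Hypoxia is not among the exceptions. Section 10.3 opens its list with "The following events count toward dose limiting toxicity (DLT) during the Phase I dose finding component", and 12.1 refers to 7.2.1 for the definition.

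**Incomplete block.** A further criterion in all three lists is "Inability to complete at least one block of three 24 hour infusions due to any treatment emergent, treatment related toxicity". Section 7.1 gives each block four 24-hour infusions.

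**50% step.** In the Schema, fever or tachycardia in one patient reduces later increases to 50%. Section 7.2.1 gives the same consequence but adds any DLT as a trigger. Both describe the 50% step as replacing a doubling. The 7.2.1 example starts from Level 4 (50 µg/kg/day), arrives at 75 and 115, and gives the unadjusted Level 6 as 200. The table in the same section gives Level 6 as 150 and Level 7 as 200.

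**CRM prior.** Section 12.1 lists prior means for six doses. A 2021 insertion gives 17% for 150 µg/kg/day and calls it an expected true probability.

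**The concern.** The DLT count is the only outcome the CRM uses, and the Phase I primary objective is defined by it. Up to 10 sites may report. For a related Grade 3 hypoxia that resolves within 72 hours, a site following 7.3.5 records a DLT, and a statistician following 7.2.1 and 10.3 does not. Under 7.2.1 a DLT also sets the size of the next dose step, so the same event can change the next dose by a second route. The texts are circular as well: 7.3.5 sends the site to 7.5, and 7.5 takes its DLT definition from 7.2.1, where the short event does not qualify.

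**Working it through.** **1. Where the hypoxia texts differ (related Grade 3, 72 hours or less)**

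Planned infusions: 3 blocks × 4 = 12. Under 7.3.5 the hung bag is finished before stopping, so the infusion in progress counts as completed.

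| Onset | Under 7.3.5 | Under 7.2.1 / 10.3 |
|---|---|---|
| Block 1, infusions 1–2 | DLT | Probably a DLT through the incomplete-block criterion (stop after 1 or 2) |
| Block 1, infusion 3 | DLT | Stop after exactly 3: not a DLT if a block means three, a DLT if it means four |
| Other 12 − 3 = 9 infusions, and infusion-free days to Day 28 | DLT | Not a DLT |

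Related Grade 4 hypoxia, and related Grade 3 hypoxia beyond 72 hours, are DLTs in both. Read literally, unrelated Grade 3 or 4 hypoxia is a DLT only under 7.3.5. The infusion-3 row is not peculiar to hypoxia: any treatment-related stop after exactly three Block 1 infusions has two classifications.

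**2. The 50% step**

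The plan's own example reproduces: 50 × 1.5 = 75; 75 × 1.5 = 112.5, rounded up to the nearest 5 = 115.

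| From (µg/kg/day) | Table step | 50% step, rounded up to nearest 5 |
|---|---|---|
| 5 | 10 (+100%) | 10 |
| 10 | 25 (+150%) | 15 |
| 25 | 50 (+100%) | 40 |
| 50 | 100 (+100%) | 75 |
| 100 | 150 (+50%) | 150 |
| 150 | 200 (+33%) | 225 |

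Only 3 of the 6 table steps are doublings. From 150 the literal 50% step is larger than the table step and exceeds the top level of 200. With 1/2 DLTs at Level 4 and no fever or tachycardia, the next dose is 75 under 7.2.1 and 100 under the Schema.

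**3. What one reclassified event does to the CRM (illustrative)**

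Inputs from 12.1: P(DLT at dose i) = dᵢ^exp(α), α ~ N(0, variance 0.5), target 20%, cohorts of 2, no skipping when escalating, prior means 3, 5, 7, 10, 14 and 20%. Assumption: 17% is the skeleton value at 150, giving 3/5/7/10/14/17/20%. The next level is the one whose estimate is closest to 20%, computed both by plugging in the posterior mean of α and by the posterior mean of P. Scenarios have 2 patients per level and no DLT below the first one named.

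*Lone first DLT, 0/2 versus 1/2.* The next level is the same at Levels 3 to 7 by both estimates. It differs at Level 1 (2 versus 1) and, with the posterior-mean estimate only, at Level 2 (3 versus 2). At Level 4 the plug-in estimate for 50 µg/kg/day moves from 3.0% to 14.5%, but both results lead to Level 5.

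*One earlier DLT (1/2), then 0/2 versus 1/2 at the next level up.* Both estimates agree:

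| Earlier DLT | Current level | Next level, 0/2 | Next level, 1/2 |
|---|---|---|---|
| Level 4 | 5 | 6 | 4 |
| Level 5 | 6 | 7 | 5 |
| Level 6 | 7 | 7 | 6 |

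Example, second row with 1/2: the plug-in estimates are 19.6% at Level 5 and 23.0% at Level 6, so Level 5 is nearest to 20%. Without the Level 5 event they are 11.6% and 14.4%, and the next cohort goes to Level 7.

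**The case against.** **The documents nearly settle which text governs the count.** Section 10.3 lists what counts and 12.1 points to 7.2.1, while 7.3.5 is toxicity management whose action is to stop treatment. The 06/01/2021 revision entry clarified the 72-hour wording in the synopsis, 7.2.1 and 10.3 without listing 7.3.5, so 7.3.5 may simply not have been updated. This makes a divergent count less likely. It does not remove it: 7.3.5 uses the defined term DLT without qualification, and no precedence is stated.

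**One event rarely matters alone.** This stands. A reader might infer that a single disputed hypoxia would redirect the dose search. At Levels 3 to 7 it does not without another DLT, and the documents report none.

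**The incomplete-block conflict is narrow.** It is. It affects only a stop after exactly three Block 1 infusions, although finishing the hung bag can produce exactly that case.

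**Tumor lysis.** A reader might see a further contradiction between "Any Grade 4 or 5 non-hematologic events" and "Grade 3 or 4 Tumor Lysis Syndrome that does not resolve within 7 days with or without intervention". The second is naturally read as the specific rule for that event, so the documents do not support calling it a conflict.

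**The 75-versus-100 case may be past.** The 05/07/2021 revision entry suggests that 100 µg/kg/day had been reached, so this case would arise only on re-escalation, and from 100 both rules give 150. A reader might infer that the trigger difference no longer matters. That does not follow, because from 150 the two figures are 225 and 200.

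**Conclusion.** The text is wrong as written. It is an internal inconsistency, not a design choice, and should be corrected. Treatment-related Grade 3 hypoxia of 72 hours or less is a DLT in 7.3.5 and not in the Schema, 7.2.1 or 10.3, unless it stops Block 1 early enough to meet the incomplete-block criterion. The three-versus-four wording and the 50% rule (trigger, doubling language, worked example) also conflict.

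The size is conditional. Once another DLT has occurred, one reclassified event moves the next cohort by one or two levels in the scenarios run; otherwise it usually moves nothing. These figures rest on assumed cohort data, and any that treat at or assign Level 6 rest on reading 17% as the skeleton value, which 12.1 does not say. They show what one reclassification does, not how often it occurs.

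**What to change.** 1. Reconcile 7.3.5, on both duration and relatedness, and the three-infusion wording with the DLT definition in the Schema, 7.2.1 and 10.3, so that each event has one classification.
2. Reconcile the trigger, the doubling language and the worked example of the 50% rule across the Schema, 7.2.1 and the seven-level table, including what the rule means from 150.
3. Secondary: in 12.1, replace the six-dose prior list with one seven-level list that says whether 17% is the prior value at 150. If the 50% rule can assign doses outside the table, such as 75 or 115, say how the CRM handles them.

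The sponsor and investigators choose the clinical rule in each case. Items 1 and 2 cost amendment wording only, with no new patients or procedures. Item 3 is wording for the seven levels. Off-table doses would need some clinician and statistician work, because 12.1 bases the priors on clinicians' estimates and set the prior variance by simulation.

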## 7.5 Duration of Study Treatment

Patients will receive one treatment course consisting of three sets (blocks) of four consecutive 24 hour continuous infusions GTB-3550 TriKE unless:

- the patient experiences the equivalent of a dose limiting toxicity (see [Section 7.2.1](#) for definition),
- the patient is unable to start Block #2 or #3 within 1 week of the planned date,
- the patient refuses further treatment,
- **Disease based treatment decisions:** If after completing Block #1 and Block #2, the patient has clear evidence of disease progression they will be discontinued from study treatment and further treatment with study drug is to be discontinued.
- In the opinion of the treating investigator, continuing treatment is not in the best interest of the patient.

For patients discontinuing prior to completing 3 blocks, post-treatment activities at Day 22 and Day 29 are shifted earlier to maintain the timing (i.e. 1 and 2 weeks from the start of the final block).

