## Appendix VI - Targeted Expected Toxicities Worksheet

HM2015-39

CTCAE v5

Refer to [Section 10.2](#) for time points

Patient Initials: \_\_\_\_\_

Date of Assessment: \_\_\_\_\_

Assessment Time Point: \_\_\_\_\_

Toxicity	Grade 0	Grade 1	Grade 2	Grade 3	Grade 4
Infusion related reaction	None	Mild transient reaction; infusion interruption not indicated; intervention not indicated	Therapy or infusion interrupt ion indicated but responds promptly to symptomatic treatment (e.g., antihistamines, NSAIDS, narcotics, IV fluids); prophylactic medications indicated for $\leq$ 24 hrs	Prolonged (e.g., not rapidly responsive to symptomatic medication and/or brief interrupt ion of infusion); recurrence of symptoms following initial improvement; hospitalization indicated for clinical sequelae	Life-threatening consequences; urgent intervention indicated
Dyspnea	None or no change	Shortness of breath with moderate exertion	Shortness of breath with minimal exertion; limiting instrumental ADL	Shortness of breath at rest; limiting self care ADL	Life-threatening consequences; urgent intervention indicated
Hypoxia	None		Decreased O 2 saturation with exercise (e.g., pulse oximeter $<$ 88%) intermittent supplemental oxygen	Decreased oxygen saturation at rest (e.g., pulse oximeter $<$ 88% or PaO 2 $\leq$ 55 mm Hg)	Life-threatening airway compromise; urgent intervention indicated (e.g., tracheotomy or intubation)
Fever*	None	38.0 - 39.0°C (100.4 - 102.2°F)	> 39.0 - 40.0°C (102.3 - 104.0°F)	> 40.0°C (>104.0°F) for $\leq$ 24 hrs	> 40.0°C (>104.0°F) for > 24 hrs
Tachycardia*	None	Asymptomatic, intervention not indicated	Non-urgent medical intervention indicated	Medical intervention or hospitalization indicated	Life-threatening and urgent intervention indicated
Chills	None	Mild sensation of cold; shivering; chattering of teeth	Moderate tremor of the entire body; narcotics indicated	Severe or prolonged, not responsive to narcotics	

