Hypertension	None	Pre-hypertension (systolic BP 120 - 139 mm Hg or diastolic BP 80 - 89 mm Hg)	Stage 1 hypertension (systolic BP 140 - 159 mm Hg or diastolic BP 90 - 99 mm Hg); medical intervention indicated; recurrent or persistent $\geq$ 24 hrs; symptomatic increase by $>20$ mm Hg (diastolic) or to $>140/90$ mm Hg if previously WNL; monotherapy indicated.	Stage 2 hypertension (systolic BP $\geq$ 160 mm Hg or diastolic BP $\geq$ 100 mm Hg); medical intervention indicated; more than one drug or more intensive therapy than previously used indicated.	Life-threatening consequences (e.g., malignant hypertension, transient or permanent neurologic deficit, hypertensive crisis); urgent intervention indicated.
Hypotension	None	Asymptomatic, intervention not indicated	Non-urgent medical intervention indicated	Medical intervention or hospitalization indicated	Life-threatening and urgent intervention indicated
Edema	None	Localized to dependent areas, no disability or functional impairment	Moderate localized edema and intervention indicated; limiting instrumental ADL	Severe localized edema and intervention indicated; limiting self care ADL	
Pneumonitis	None	Asymptomatic; clinical or diagnostic observations only; intervention not indicated	Symptomatic; medical intervention indicated; limiting instrumental ADL	Severe symptoms; limiting self care ADL; oxygen indicated	Life-threatening respiratory compromise; urgent intervention indicated (e.g. intubation or tracheotomy)
Headache	None	Mild pain	Moderate pain; limiting instrumental ADL	Severe pain; limiting self care ADL	
Confusion (Altered Mental Status)	None	Mild disorientation	Moderate disorientation; limiting instrumental ADL	Severe disorientation; limiting self care ADL	Life-threatening consequences; urgent intervention indicated
Rash	None	Covering < 10% body surface area (BSA)	Covering 10-30% body surface area (BSA)	>30% body surface area (BSA)	Generalized exfoliative, ulcerative, or bullous dermatitis
Gait Disturbance	None	Mild change in gait (eg, wide-based, limping or hobbling)	Moderate change in gait (eg, wide-based, limping or hobbling); assistance device indicated; limiting instrumental ADL	Disabling; limiting self care ADL	
Ataxia (Incoordination)	None	Asymptomatic; clinical or diagnostic observations only; intervention not indicated	Moderate symptoms; limiting instrumental ADL	Severe symptoms; limiting self care ADL; mechanical assistance indicated	

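### For Grade 4 hypoxia, Section 7.3.5 should stop the running infusion instead of letting the hung bag finish

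*Combined protocol and SAP*

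**What the plan says.** Section 7.3.5 sets its threshold at Grade 3 hypoxia, a resting saturation below 88%, and continues: "or higher is a dose limiting toxicity. In this situation, discontinue treatment for per" Section 7.5. The timing attached to that instruction is "after completion of the currently hung infusion bag, if applicable". There is no separate line for Grade 4.

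In Appendix VI, the Grade 4 entry for hypoxia reads "Life-threatening airway compromise; urgent intervention indicated (e.g., tracheotomy or intubation"). Pneumonitis has its own row, with Grade 4 given as "Life-threatening respiratory compromise; urgent intervention indicated (e.g. intubation or tracheotomy"). Both rows are separate from the row for infusion related reaction.

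The DLT list in Section 7.2.1 covers related, treatment-emergent events within 28 days of the first dose and includes "Any Grade 4 or 5 non-hematologic events". The note in Section 7.3 adds: "Any patient experiencing a DLT equivalent toxicity must discontinue treatment per" Section 7.5.

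Two other provisions can end an infusion sooner. Section 7.3.2, which watches for hypotension, dyspnea and angioedema, says "The infusion will be stopped and the reaction treated per" Section 7.1. Section 7.5 ends the course on this ground among others: "In the opinion of the treating investigator, continuing treatment is not in the best interest of the patient".

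**The concern.** A patient with Grade 4 hypoxia may be about to be intubated. Read literally, the only section written for that event tells staff to let study drug run until the bag is empty. The patient will receive no further bags, so the protocol gains no later treatment from the delay, and it gives no reason for it. What is at stake is continued exposure to an investigational agent during a life-threatening event, at any of up to 10 sites working from the same text. This is a patient-safety matter. It does not touch sample size, power or error rates.

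**Working it through.** **1. The grade rules side by side.**

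| Event | Grade 3 | Grade 4 |
|---|---|---|
| Liver tests (7.3.3) | Hung bag may finish; rest of the block omitted | Permanent discontinuation; no bag allowance |
| Infusion related reaction (7.1, 7.3.2) | Infusion stopped; permanent discontinuation | Same |
| Hypoxia (7.3.5) | Hung bag may finish; then off treatment | Same as Grade 3 |

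Hypoxia is the only row in which the bag allowance reaches Grade 4. Section 7.3.3 does not say in terms that a running bag is pulled at Grade 4, but it attaches the allowance to Grade 3 alone.

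**2. Does any other text create a Grade 4 exception?** The closing words of the bag instruction most naturally mean that it applies if a bag is hanging; they do not separate grades. The 7.3 note and Section 7.5 say that treatment ends, not when the running bag stops. The CRS section (7.3.6) has no instruction to stop the infusion. What remains is the reaction rule in 7.1 and 7.3.2 and the investigator's discretion in 7.5.

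**3. Size of the extra exposure.** Inputs: 100 mL per bag at 4.17 mL/h (7.1); 3 blocks of 4 bags (7.1); 5 µg/kg/day at Level 1 and 200 µg/kg/day at Level 7 (7.2.1); pulse oximetry times for infusions 2 to 4 of a block (7.1.1).

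- Bag run time: 100 / 4.17 = 23.98 h, which agrees with the stated 24 h.
- Share of the course: 3 × 4 = 12 bags; 1/12 = 8.3%.
- Hourly dose: 200/24 = 8.33 µg/kg/h at Level 7; 5/24 = 0.208 µg/kg/h at Level 1.
- The nominal checks fall at 15, 30, 45 and 60 min, then at 5, 9, 13, 17 and 21 h.
- Event found at the first check (0.25 h): 24 − 0.25 = 23.75 h left, or 23.75 × 8.33 = 198 µg/kg at Level 7 and 23.75 × 0.208 = 4.9 µg/kg at Level 1.
- Event found at the last check (21 h): 3 h left, or 25 µg/kg at Level 7 and 0.6 µg/kg at Level 1.

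The range is therefore 0 to 24 h, or 0 to one daily dose.

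**4. Effect of an immediate stop on how patients are counted.** Section 12.1 ties DLT evaluability to completing Block #1 and replacement to completing Blocks #1 and #2. In bags 1 to 3, Block #1 is left incomplete under either wording, because 7.3.5 already ends treatment. Only the last bag of Block #1 or Block #2 (bag 4 or bag 8, 2 of 12) could change whether a block is complete. A related Grade 4 event in Block #1 is a DLT under 7.2.1 whether or not the bag finishes.

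**The case against.** The strongest reply is that the infusion would in practice be stopped. Dyspnea is a named trigger in 7.3.2, and most patients with airway compromise would be expected to be short of breath, although that is a clinical inference. All treatment is inpatient, and 7.3.5 itself refers to 7.5, where the investigator may end treatment at any time. Harm would require a team to manage an intubation and still keep the drug running. On this view, 24 h is a literal upper bound and not a likely exposure.

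Most of this stands, and it narrows the point. It does not remove it. Section 7.3.2 applies to reactions and does not name hypoxia, while Appendix VI expects hypoxia and pneumonitis as events in their own right. The discretion in 7.5 carries no timing, whereas 7.3.5 gives an explicit one. A written default to continue should not depend on staff overriding it.

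A reader might go further and infer that the infusion must also stop at once for Grade 3 hypoxia, particularly as 7.1.5 requires a saturation of at least 88% to begin a new block. The documents do not support that as a correction. The 7.1.5 threshold governs starting a block. Letting the bag finish at Grade 3 is a choice the protocol also makes in 7.3.3. Although 7.3.5 calls Grade 3 hypoxia a DLT outright, 7.2.1 counts a Grade 3 non-hematologic event only if it is related and lasts beyond 72 hours, which a new desaturation cannot do within the 24 h or less left in a bag.

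**Conclusion.** The point holds for Grade 4 hypoxia only: as written, 7.3.5 lets the hung bag finish during an event that the protocol itself grades as life-threatening. It applies where the event is not handled as an infusion related reaction and the investigator has not stopped the drug under 7.5. The wording should be corrected.

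The excess is at most one daily dose per affected patient. This takes the check times as nominal, ignoring their ±10 and ±20 minute windows. The documents give no incidence of hypoxia, so neither an expected number of cases nor an average exposure can be stated. The rule is not limited to one phase, so it governs all treated patients (Section 12.3 expects about 44 and allows up to 57). That is the number under the rule, not the number affected.

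A reader might also infer that Section 12.1 needs a clause treating a block cut short for hypoxia as complete. The documents do not support this. Such a clause would alter the evaluability and replacement rules for one event type and leave patients stopped for reactions or Grade 4 liver tests under the existing rule. A related Grade 4 event is already a DLT under 7.2.1.

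**What to change.** Limit the hung-bag allowance in 7.3.5 to Grade 3 and add: *For Grade 4 hypoxia, stop the running infusion immediately and permanently discontinue study drug per Section 7.5; do not complete the hung bag. Sections 7.1 and 7.3.2 govern if an infusion related reaction is present.*

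The cost is a wording change and a memo to sites, with no added procedures. An affected patient loses at most part of one of the 12 daily doses. If the stop falls in bag 8, Block #2 would be incomplete and the existing replacement rule in 12.1 could apply; this is a small consequence to accept, not a reason to finish the bag.
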